6 STUDY SETTING

All of the phases of this project will each be multicentre, using 2, 2 and 4 professional football clubs respectively in North West England. The majority of the study activities will be carried out within these premises. These activities include:

Phase 1: 2 Focus groups in two different clubs

Phase 2: Delivery of intervention in two different clubs

Coach training in two different clubs

Post programme focus groups

Phase 3: Delivery of the intervention in four different clubs

For the pilot RCT, we will recruit four clubs with different characteristics to test our procedures in a range of settings. We require: a) at least one club with a primary betting partner and at least one with little/no gambling sponsorship; b) at least one urban/city-based club and at least one suburban club; e) at least one larger club (attendance at home games >20,000 people) and a smaller club (attendance at home games <20,000). To date we have secured support from two clubs: Everton FC, a large premier league club based in an urban area which currently has Sport Pesa (an online gambling company) as its primary sponsor; and Fleetwood Town FC, a small club in Football League 1 situated in a suburban/rural area of the North West which currently has no official gambling partnership.

7 SAMPLE AND RECRUITMENT

7.1 Eligibility Criteria

Our target population is regular male sports bettors who feel their gambling may be affecting their health, wellbeing or relationships *and* who would like to make positive steps to change their gambling behaviour.

7.1.1 Inclusion criteria

- 1. Males aged 18-44.
- 2. Self-reported sports bettors (at least once a week).
- 3. Express an interest in reducing their involvement in gambling in the context of improving their health and wellbeing.
- 4. Can commit to attending sessions once a week for nine weeks.

7.1.2 Exclusion criteria

- 1. Females
- 2. Males < 18 or > 44 years old
- 3. Problem gambler, identified using the Problem Gambling Severity (PGSI) miniscreen (score of more than 4).
- 4. Cannot read/speak sufficient English to give informed consent

Men who are excluded from the study on the basis of being a problem gambler will be signposted to services for support and treatment.

7.2 Sampling

Phase 1: We will aim to recruit approx. 12- 16 men for the focus groups (n=6-8 at each group)

Phase 2: We will aim to recruit approx. 30 male sports bettors for each of the feasibility deliveries in Phase 2 (n=15 at each club).

Phase 3: We aim to recruit 120 male sports bettors (n=30 at each club) to the pilot RCT trial.

7.2.1 Size of sample

Guidance for pilot studies varies [18,19]. We will work with four football clubs in the North West of England, each recruiting 30 participants (60 per arm) to achieve a target sample size for the pilot RCT of 120. The retention rate in FFIT was high, exceeding 90% at 12 weeks and 12 months [16]. Allowing for slightly lower retention (80%), we would still have 96 participants with follow up data.

7.2.2 Sampling technique

For all phases, our sample will reflect our target population: men aged 18-44 who want to reduce their gambling. The sampling methodology will be a mix of convenience sampling with other methods like snowballing should recruitment prove more difficult than anticipated. For all phases, participants will be asked to opt-in to the study.

Convenience sampling is appropriate for all phases of the study as it allows easy access to a potentially hard to reach target audience, using the available mechanisms at the club to advertise and recruit participants.

The clubs themselves are purposively sampled based on the following criteria: a) at least one club with a primary betting partner and at least one with little/no gambling sponsorship; b) at least one urban/city-based club and at least one suburban club; e) at least one larger club (attendance at home games >20,000 people) and a smaller club (attendance at home games <20,000).

7.3 Recruitment

Approach: Building on insight gained in Phases 1 and 2, clubs (supported by Healthy Stadia) will use a range of recruitment strategies, including advertisements via the club's social media and at the club's ground, use of local fan networks and community groups, and advertising on local media to advertise and recruit to the study. Where data protection rules and club permissions permit, clubs will send direct recruitment material via email and post to potential participants.

- We intend to utilize the existing community and fan programmes that are run by football Clubs in both the Premier League and lower divisions as vehicles to refer men on to FFAB. Clubs have a wide range of these programmes, such as EuroFIT, Man V Fat, walking football, health checks and wider wellbeing programmes for men and family units and they have advised us that they are confident that these can be utilized effectively to attract participants. We anticipate that a minimum of 30% of men will be successfully recruited to FFAB through this method.
- In addition, most Clubs have strong links with local organizations who employ large numbers of men (e.g. bus or taxi companies, Royal Mail, warehousing), and these are an excellent way of recruiting participants to gender-sensitised programmes. Healthy Stadia will be able to work closely with each club foundation to ensure that these referral pathways are maximized to meet recruitment targets.
- We will also draw on the communications apparatus that Clubs have at their disposal. The infrastructure that Clubs have to engage and recruit men is extremely effective. For example, Everton FC (one of our pilot clubs) has a 'community database' of over 50,000 people. If we assume that 30% of those on the database are men aged 16-44 and that at least one third are regular gamblers, this gives an initial target population of c.5000 men from which to recruit 30 participants. Clubs will send direct recruitment material via email and post to potential participants
- We will use a range of materials and media to recruit men to the programme. We have budgeted for a professional design company to produce and print a range of FFAB branded recruitment materials. The FFAB 'brand' and logo will be specifically designed to appeal to our target group, and will be developed by the project codevelopment group, made up of team members, PPI Cis, as well as a football fan and a recovered problem gambler. The visual imagery will be used consistently across a range of media, including flyers and posters, and will be distributed widely to advertise and recruit to the programme. We intend to develop a project website and linked social media accounts, and will also target local community media networks and organisations, as well as Football Club grounds.

Process: The process of recruitment will be informed by learning from the Standard Operating Procedure (SOP) of the EuroFIT programme, which will be adapted for the specific context of FFAB.

- Planning: we will allow approximately 3 4 weeks to promote the programme before enrolment begins. We will work with Clubs to plan how best to promote FFAB through their community and fan programmes, as well as locally, focusing on where, how and when is best to do this, and what materials are needed.
- *Targeting*: we will discuss with Clubs which strategies to use and where to target. These will include:
 - Club-based venues, organisations and activities
 - Posters/flyers in Club
 - Posters/ flyers in community programmes
 - Advertisement on club/trust/fans website
 - Club/community trust twitter feed/ Facebook
 - Direct email to club fans with recruitment message
 - Announcement in fan newsletters
 - Match-day advertising, with a recruitment team in attendance to hand-out leaflets and collect contact details

- Match-day programme advert and in-stadia announcements
- Local Media
 - Newspapers (local, regional, national), radio and TV coverage
- Other local organisations
 - Local employers (eg bus and taxi companies, warehousing, Royal Mail, community centres)

Recruitment text: a clear recruitment message, to be included on all recruitment materials, will be produced by the development group. It will explain the programme and outline the inclusion criteria. We will set up a single project contact email address and mobile phone number which will be included on all materials.

FFAB website: A project website will be established and linked to all participating organisations, including Clubs. Information about the programme and contact details for potential participants will be included.

7.3.1 Sample identification

For all phases, participants will self-identify and opt-in to the project by responding to recruitment advertising co-developed with clubs and the project teams.

A multimedia recruitment strategy will be developed and will include social media posts, posters and leaflets, all of which will provide instructions on how to join the study and necessary contact details. The football clubs and study partners will design and execute a co-developed recruitment strategy that makes use of these materials.

Interested participants who make contact with the study team will be asked a series of questions to screen for eligibility. This will aim to identify men who are: aged 18-44; self-report that they bet on sports at least once a week; express an interest in reducing their involvement in gambling and say they can commit to attending sessions once a week for nine weeks. At this point, men will also be screened to determine their gambling status, using the Problem Gambling Severity Index (PGSI) mini screening questionnaire. A score of 4 or more would indicate that they might have a gambling problem, and if this were the case, the potential participant would not be included in the study, but would be directed towards further information to self – refer to sources of advice and treatment offered by our expert partners.

Participants who take part in focus groups and/or in-depth interviews will be offered a £20 voucher to thank them for their time. Participants who take part in the full FFAB feasibility test or the pilot RCT will be offered £20 voucher to thank them for their time.

7.3.2 Consent

Informed consent will be obtained from all individuals before participation in the study. During recruitment, they will be provided with an information sheet, which outlines the purpose of the research, their potential role in it, and explains that participation is entirely voluntary, confidential, and can be stopped at any time. It will also have information about sources of further information, and of support and help. The information sheet will be

received at least 24 hours (either in person or via email) before the informed consent procedure.

The informed consent procedure will be conducted by a trained member of the research team, who will explain the the aims of the research, its benefits and potential risks, to ensure potential participants fully understand what participation in the study will involve. They will have the opportunity to ask questions, and to discuss any aspect of the research with the research team member.

Before signing consent forms, a trained member of the research team will ensure that they are satisfied all participants are fully informed and understand the nature and purpose of study.

8 ETHICAL AND REGULATORY CONSIDERATIONS

The research aims and methods are designed to develop an intervention that will help a population group at high risk of gambling related harm to reduce their involvement in gambling, and also to improve their overall wellbeing. The research process is guided by the principles of informed consent, participatory collaboration, and of doing no harm to participants. We have built in robust safeguards to uphold the wellbeing and dignity of participants at each stage of the research process.

We believe that the benefits to gamblers, their families and communities and society as a whole outweigh any possible inconvenience or discomfort to participants during the course of the study. Ultimately, the FFAB programme has the potential to reduce gambling-related harms and increase health and wellbeing among our target population. If successful, this will reduce the burden of gambling on the NHS and society. Our project will assess this potential and, should results look positive, then we will move to a full-scale trial to provide the most robust evidence of effectiveness and cost-effectiveness.

8.1 Assessment and management of risk

Risk/ Potential risks of the study. We are aware that gambling can be a sensitive topic, and that asking men to talk about their attitudes about it could involve bringing up issues of compulsive behaviour, mental health issues and financial problems, and could be distressing for some. Discussing gambling in a group context could encourage some participants to reflect on their own behaviour, and may generate feelings of shame or stigma, or prompt some to think they may have a gambling problem. Unanticipated outcomes could include participation in the study enabling a partner/family member to realize that the participant was involved in gambling, and precipitating rows/relationship breakup, or causing them to drink more to cope with the worry. For some, it could increase feelings of shame or guilt as the participant realizes the broader impact of their gambling on others, or the extent to which gambling has limited their range of engagement in other things. Non-gambling related outcomes could relate to sustaining an injury as a result of increased involvement in physical activity as a consequence of

taking part in FFAB. Throughout the project, we will explore the consequences of taking part in the study within all qualitative interviews with participants and coaches.

Risk management plan for risks of harm to participant./ others: The project team are aware of the potential for distress that could arise from discussing gambling. We have made use of the extensive experience within our team to mitigate it. Academic members of the team have experience in designing health-based interventions around sensitive topics (eg weight loss), while the gambling behaviour organisations have experience of dealing with issues related to gambling harms and mental health. We are confident that the co-development of the research, and its ongoing monitoring by these individuals and groups, will work to minimise risk and safeguard participants wellbeing.

To this end, we have built in safeguards at each step of participants' trajectory through the research.

- During recruitment, to ensure that participants understand the research and what it involves, participants will be provided with an information sheet and consent form which clearly explains the aims of the project, and their role in it. From the outset, this will include the details of project partners Betknowmore and Beacon Counselling Trust, as well as details of other organisations, including GamCare, a national treatment provider who have specialist online forums, chatrooms and a 24 hour helpline phone number. Discussion and questions about the research will be encouraged, to ensure that clear communication is established with the researcher, allowing for informed consent to be given.
- Before and during the sessions themselves, researchers will explain to participants that they do not have to participate in discussions/ respond to questions if they do not want to, and that if they become uncomfortable at any time, they are free to stop participating/ leave the group. Researchers will also be sensitive to the impacts of discussions during the focus groups and will monitor participants for signs of distress throughout. Being mindful of the group context of discussions, they will take steps to pause it if they feel that a participant needs a break, or if they wish to end the session. Researchers will be vigilant for signs of any psychological, emotional or other issues that may arise at any point during the study, and will be prepared to signpost/ refer an individual to sources of support if necessary. While coaches will be trained to ensure participants exercise within their limits, and how to respond when any injuries occur, any injuries that are sustained during the physical activity component of the project will be reported by coaches to the research team, as an adverse/serious adverse event.
- Throughout and at the end of discussions, details of organisations who provide support for a range of issues related to gambling, mental health and other problems, will be made available for participants who might wish to discuss anything further. These will be listed on the Participant Information Sheet. At the end of the session, participants will be thanked for their input and reminded of this list of organisations.

Risk management plan: We have identified a referral procedure for dealing with safeguarding issues. It has been guided by our CI partner, [name], Clinical Director of the Beacon Counselling Trust. As well as being a specialist gambling treatment provider,

the Trust is also one of the largest mental health support providers across the North West of England, engaging with over 3500 patients per year. [name] has advised on adapting the Trust's protocol for referrals to the current study. As such, should any participant disclose to any team member as experiencing psychological, health or emotional issues during the study, or be identified by a team member as experiencing them, they will be offered an immediate referral for initial assessment at Beacon. There, they will be seen by a trained professional, who will make an assessment of their needs and identify the most appropriate next steps. This may involve continued care from Beacon therapeutic staff, or a referral into another, more appropriate service, which would be facilitated by Beacon. This process would be carried out following a standard care pathway, and in collaboration with the individual concerned.

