RQ12. What are the optimum methods for follow-up data collection?

RQ13. Are there other intended and unintended (positive or adverse) consequences?

RQ14. Is it feasible to collect data on the relevant costs and consequences associated with gambling and potential pathways between gambling and its associated costs and outcomes over the short and long term?

RQ15. Does the FFAB logic model need refinement?

RQ16. Do the findings warrant a full scale RCT of the FFAB programme?

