Gambling involvement will be measured on two domains: breadth and depth [36, 40] and will be captured using validated measures of gambling involvement: number of different types of gambling activities undertaken (breadth) and self-reported gambling frequency (total number of bets placed, number of days spent gambling); total money spent on gambling; and total time spent on gambling (depth). All of these questions were developed and tested for the British Gambling Prevalence Survey 2010 [36]. Their validity and reliability have been assessed, showing good to excellent reliability and validity [41] when compared with diary methods.

Proposed **secondary outcome measures** include specific items from the DSM-5 problem gambling screening instrument pertinent to our intervention (such as betting more than one could afford to lose, trying and failing to cut back on gambling, gambling as escapism and being restless or irritable when trying to cut back on gambling) [42]; a measure of social support, (an adapted version of the Shortened Social Support Scale

made appropriate for gambling and perceived social support more generally) [43]; and Rosenberg's Self Esteem Scale [44].

We will collect information on attendance and logged data of app diary usage. If data quality permits, we will use data from the app to help inform progress towards reductions in gambling involvement (RQs7,12). Analysis of app data will be done post-intervention. We will conduct focus groups with intervention participants after they have completed the intervention to understand their experiences of FFAB, of making and sustaining reduction in their gambling behaviours, and of the research procedures (RQs8&10). Post intervention, we will conduct exit interviews with non-completers, and interviews with coaches and football club representatives to understand their views and experiences of delivering FFAB and of involvement in the pilot (RQs5,6,8,9).

5 STUDY DESIGN and METHODS of DATA COLLECTION AND DATA ANALYIS

The research design is a mixed methods feasibility study and pilot multi-site parallel group RCT. It comprises three phases, corresponding to our three main research objectives.

Phase 1. Refinement of FFAB for initial delivery (months 0-6)

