Procedures	Visits (insert visit numbers as appropriate					priate)
	Screening	Baseline	Weeks 1-9	Week 10	6 months	12 months
Phase 2						
Informed consent	Х					
Observation of treatment			x			
Focus Group with completors/coaches				х		
Exit interviews with non-completors				х		
Phase 3						
Informed consent	х					
Demographics		Х				
Medical history/outcome measures		х				
Observation of treatment			х			
Focus groups with completors				х		
Exit interview with non-completors				х		
Outcome measures data collected				х	х	х

13 Appendix 3 – Amendment History

Amendment No.	Protocol version no.	Date issued	Author(s) of changes	Details of changes made

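### For RQ13, the enquiry the protocol describes into relationship break-up, heavier drinking and injury is confined to the intervention arm; unless forms not shown already ask about them, the pilot will have no control-arm or 6- and 12-month data on these events

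*Protocol*

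**What the plan says.** Section 4.1 lists, among the Phase 3 questions, "RQ13. Are there other intended and unintended (positive or adverse) consequences". Section 8.1 then names possible harms. For relationships and alcohol, it describes a partner learning of the gambling, "precipitating rows/relationship breakup, or causing them to drink more to cope with the worry". It also names injury from increased physical activity. Its stated enquiry is that "we will explore the consequences of taking part in the study within all qualitative interviews with participants and coaches".

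The Phase 3 contacts that could carry this enquiry are:

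- **Focus groups** (4.2): "We will conduct focus groups with intervention participants after they have completed the intervention". Appendix 2 schedules them at week 10.
- **Interviews** (4.2): "Post intervention, we will conduct exit interviews with non-completers, and interviews with coaches and football club representatives". Appendix 2 puts the row "Exit interview with non-completors" at week 10. The coach and club interviews have no row there and are dated only as post-intervention.
- **Observation of sessions**: weeks 1 to 9 (Appendix 2).
- **Injury reports** (8.1): "any injuries that are sustained during the physical activity component of the project will be reported by coaches to the research team".

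A referral route is open to everyone: "should any participant disclose to any team member as experiencing psychological, health or emotional issues during the study", an immediate referral for assessment is offered (8.1).

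Section 5 (Assessment and follow-up) gives all participants the outcome questionnaire at baseline, 10 weeks, 6 months and 12 months, with 12 months as the primary time point.

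**The concern.** Relationships end, drinking changes and injuries happen without any programme. Accounts from men who received FFAB can show how such an event came about. They cannot show whether it was more frequent than it would otherwise have been. That needs the same question put to the control men, and put again at 6 and 12 months, because a break-up or a change in drinking need not appear by week 10.

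The pilot exists to try out procedures for a full trial. Section 5 (Data and statistical analysis) will report the completeness of the proposed efficacy measures at all four time points. No item on these harms is described as being tested in the same way, so the full trial could start without knowing whether men will answer such questions or what background rate to expect.

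Two other features of the protocol point the same way. The logic model (Figure 2) lists fewer relationship problems or breakdowns as a long-term outcome, yet no listed measure would record them in either direction. Section 5 also describes confidential self-completion as the best method for sensitive behaviours, whereas men who complete the programme would be asked about these matters in a group.

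**Working it through.** **Step 1. Who is asked about the three named events, and when (Phase 3, as described).**

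| Source | Arm | Timing |
|---|---|---|
| Focus groups with completers | Intervention | Week 10 |
| Exit interviews with programme non-completers | Intervention | Week 10 |
| Coach and club interviews | About the intervention | Post-intervention, not dated further |
| Session observation | Intervention | Weeks 1–9 |
| Coach injury reports | Intervention, programme activity only | During sessions |
| Referral on disclosure | Both | Any time, passive; no recording by arm described |

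No control-arm interview appears in 4.2, 5, 8.1 or Appendix 2. Section 4.2 tags the Phase 3 focus groups to RQs 8 and 10 and the interviews to RQs 5, 6, 8 and 9. No data-collection step is tagged to RQ13.

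**Step 2. What both arms answer to 12 months.** Sections 4.2 and 5 (Health economic evaluation) list WEMWBS, the ONS wellbeing items, EQ-5D, ICECAP-A, gambling involvement, selected DSM-5 items, social support, self-esteem, service use, and income and productivity. These would pick up a general decline. None names break-up, alcohol or injury. The DSM-5 and economic items are given by example and the forms are not shown, so this is an absence from the description, not proof of absence from the questionnaire.

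**Step 3. Numbers available.** The protocol's own figure (7.2.1) reproduces: 4 × 30 = 120, and 120 × 0.80 = 96, or 48 per arm at 1:1.

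**Step 4. What added items would deliver.** The protocol gives no event rates. Assume that a proportion p of men in each arm has a given event within 12 months, with p from 5% to 20%.

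- Expected events per arm: 48 × 0.05 = 2.4; 48 × 0.20 = 9.6.
- 95% half-width, arm difference: 1.96 × √(2p(1−p)/48).
- 95% half-width, control rate: 1.96 × √(p(1−p)/48).
- 95% half-width, pooled rate: 1.96 × √(p(1−p)/96).

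| p | Arm difference | Control rate | Pooled rate |
|---|---|---|---|
| 5% | 8.7 points | 6.2 | 4.4 |
| 10% | 12.0 | 8.5 | 6.0 |
| 20% | 16.0 | 11.3 | 8.0 |

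Item completeness c among 96 men, 1.96 × √(c(1−c)/96): 8.0 points at c = 80%, 6.0 at 90%, 4.4 at 95%. These values of c are also assumptions.

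**The case against.** The strongest reply has four parts.

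**The questionnaire content is not fixed in the protocol.** Secondary measures are introduced with open wording. The economic instruments are meant to cover a full range of costs and consequences, and the conceptual model includes a family layer. Appendix 2 also has a baseline row for medical history and outcome measures. A reader might infer that the data will certainly not be collected and that no analysis plan could recover them. The documents do not support that, because the forms are not shown. The point holds only if those forms lack the items.

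**RQ13 is open-ended and names no comparator.** Interviews are a legitimate way to find unforeseen consequences in a pilot, and writing structured items afterwards for the full trial is a coherent sequence. This stands: nothing in the protocol is contradicted. But the three events are already foreseen in 8.1, so structured questions could be piloted now.

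**Harm enquiry is wider than the interviews.** Researchers observe sessions and are told to watch for distress throughout, and the Phase 2 focus groups ask about unanticipated adverse outcomes. A reader might infer that harm in control men goes wholly unnoticed. That is too strong, since they complete the wellbeing measures and may use the referral route. Observation and Phase 2 are, however, uncontrolled, and the referral route is passive.

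**The fix would not give a real test between arms.** This is correct. With about 2 to 10 assumed events per arm, only a large difference would show. Moreover, 8.1 links break-up to taking part in the study, and control men also receive questionnaires and reminders. Harm caused by contact common to both arms would not appear in the difference, and the control rate would not be a pure background rate.

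**Conclusion.** The point holds in a limited form. As described, enquiry into the three named events is in the intervention arm only, with the scheduled participant enquiry at week 10. Unless the unseen forms already ask about them, the pilot would have no control-arm rate, no 6- or 12-month data on these events, and no evidence on whether harm items are completed.

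The size of the gain is modest. At 80% retention and assumed rates of 5% to 20%, the control rate would be known to within about 6 to 11 points, the pooled rate to within 4 to 8, and the arm difference only to within 9 to 16. Completeness of 80% to 95% would be known to within 8 to 4 points. The comparison by arm is therefore descriptive, and the background rate and completeness figure are the more useful products.

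No primary aim, sample size or efficacy analysis is affected. I would ask the sponsor to consider the change.

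**What to change.** 1. In 4.2, either confirm that the both-arm forms already hold items on these events or add three or four identical self-report items (separation, change in drinking, injury needing care) to the existing outcome questionnaire. Ask both arms at week 10, 6 months and 12 months, with a baseline drinking item.
2. Tabulate the items by arm with 95% confidence intervals as descriptive data under RQ13, and report their completeness beside that of the efficacy measures. State that a difference between arms cannot detect harm from study contact shared by both.
3. Keep the interviews and focus groups to explain how harms arise.
4. Keep the coach injury reports as a record for FFAB only, and do not compare them by arm.

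The cost is about a minute per questionnaire and short edits to 4.2 and 8.1, with no extra visits, staff or participants. The items are sensitive and need the signposting already planned, and the estimates will be imprecise and must be labelled as such.
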